3.1 Differences Statement

This is a Phase 3b study to assess the impact on quality of life of venetoclax monotherapy as a primary endpoint in relapsed or refractory CLL subjects. In this study, several PRO measures will be utilized to assess quality of life in subjects with relapsed or refractory CLL. This data will add to the quality of life data already collected from 17p deletion CLL subjects in Study M13-982.³⁵ In addition, the impact of venetoclax monotherapy on quality of life will be assessed in correlation with efficacy data (i.e., overall response rate [ORR], duration of overall response [DOR], etc). This will allow for an assessment of the relationship between quality of life and treatment outcomes in this high risk subject population.

3.2 Benefits and Risks

There is data from a previous study (Study M13-982) that shows there is substantial improvement in quality of life in addition to efficacy with venetoclax monotherapy in

subjects with relapsed/refractory CLL characterized by 17p deletion. Venetoclax is expected to be as active in subject selected for TP53 mutations as these subject populations overlap and the oncogenic effect of both genetic defects occurs via p53 abrogation. In addition, there are limited data in the BCRi failure CLL population for subjects that subsequently receive venetoclax and also in subjects without the 17p deletion. Current CLL therapies do not reliably produce complete responses and are not curative in subjects with p53 aberrations or those refractory to BCRi. Furthermore, drugs more recently approved for these subjects are limited by toxicity.

Clinical safety data indicate that the adverse effects of venetoclax administered with appropriate measures are manageable and as expected from a treatment targeting hematologic cells including in subjects with 17p, TP53 mutation or subjects who have previously received BCRi therapy.

Additional safety and efficacy data can be found in the current Venetoclax Investigator's Brochure.⁸

4.0 Study Objective

The primary objective of this study is to evaluate the impact of venetoclax monotherapy on the quality of life of subjects with relapsed or refractory chronic lymphocytic leukemia (CLL). Quality of life will be assessed by the Global Health Status/Quality of Life (GHS/QoL) subscale of the European Organization for Research and Treatment of Cancer Quality of Life Core Questionnaire (EORTC QLQ-C30).

The secondary objectives are to evaluate the impact of venetoclax monotherapy on quality of life based on the European Organization for Research and Treatment of Cancer Quality of Life Questionnaire Chronic Lymphocytic Leukemia Module (EORTC QLQ-CLL16), EuroQoL 5 Dimension 5 Level Questionnaire (EQ-5D-5L), and the remaining subscales/items from the EORTC QLQ-C30; overall response rate (ORR); complete remission rate (CR + CRi); duration of overall response (DOR), time to progression

(TTP), duration of progression-free survival (PFS); overall survival (OS); and CR rate in BCRi treated subjects.

The safety and tolerability of venetoclax in subjects with relapsed/refractory CLL will also be evaluated.

5.0 Investigational Plan

5.1 Overall Study Design and Plan: Description

This is an open-label, single arm, Phase 3b, multi-center study evaluating the impact of venetoclax monotherapy on the quality of life in relapsed/refractory CLL.

This study is designed to enroll approximately 200 subjects to meet scientific objectives without enrolling an undue number of subjects in alignment with ethical considerations. All efforts will be made to adhere to these specific enrollment numbers; however, it would not be ethical to deny treatment to eligible subjects in screening as they may have undergone study related procedures.

Subjects in this study will be enrolled at approximately 43 research sites in Latin America, Eastern Europe, and Asia-Pacific.

Subjects will undergo screening procedures within 28 days prior to initial venetoclax administration. For all subjects, a contrast computed tomography (CT) scan (or medically indicated alternative such as magnetic resonance imaging [MRI]) will be accepted if previously performed within 35 days prior to venetoclax administration. Otherwise, a CT scan (or MRI) must be performed within the screening period of 28 days. Following the 4-week Screening period, eligible subjects will initiate venetoclax and attend study visits within 72 hours of dosing and on the first and second day of Week 1 and Week 2 during the dose titration phase. Beginning on Week 3, through Week 5, study visits will be conducted within 72 hours of dosing and on Day 1 of each week. Additional study visits on Day 2 of each week should be performed for subjects who continue to be at risk for TLS, based on investigator assessment. Study visits will be reduced to a monthly

frequency at Week 8, and at Week 48, they will be reduced to every 3 months until the end of study treatment (Week 108). As of Week 8, the visit window for scheduled visits is ± 2 days. A 30 day Safety Follow-up Visit should be performed approximately 30 days (± 3 days) following the last dose of venetoclax (to allow for AE collection 30 days following last dose of study drug). If a subject is discontinued from the study with an ongoing AE or an unresolved clinically significant laboratory result, the site will attempt to provide follow-up until the AE has resolved to a \leq Grade 1 or baseline or it is the investigator's judgment that the event is unlikely to resolve.

Venetoclax will be administered orally once daily (QD), continuously. Venetoclax tablets should be taken with a meal and water in the morning at approximately the same time each day. To mitigate the risk for TLS, the first 5 weeks of treatment include a dose-titration phase where venetoclax will be dosed in increments as outlined in [Figure 1](#). The starting dose of venetoclax is 20 mg once daily. The dose will be gradually increased over a period of 5 weeks up to the daily dose of 400 mg.

Figure 1. 5-Week Dose-Titration Schedule

Week	VENETOCLAX Daily Dose
1	20 mg
2	50 mg
3	100 mg
4	200 mg
5 and beyond	400 mg

Disease response will be assessed by the investigator based on laboratory results and physical examinations using the 2008 Modified International Workshop on CLL National Cancer Institute – Working Group (IWCLL NCI-WG) Guidelines for Tumor Response with the addition of CT imaging (or MRI). Quality of Life Assessments will be performed within 72 hours prior to the first dose of venetoclax and at Week 4, Week 8, Week 12, Week 24, Week 36, and Week 48, then every 12 weeks thereafter until the end of study treatment (Week 108). A Disease Assessment for clinical response by physical

exam and hematologic assessments will be performed at Screening, Week 24, Week 36 and Week 48. To confirm the response, a CT scan (or MRI if CT is medically contraindicated) will be performed at Week 48 on all subjects and BM samples will be collected for subjects with CR to confirm the response.

When confirming a CR or Cri status per the 2008 IWCLL NCI-WG guidelines, a bone marrow biopsy and aspirate should also be performed.

Quality of life will primarily be assessed by using the GHS/QoL subscale of the EORTC QLQ-C30. Secondary objectives will evaluate the quality of life based on the EORTC QLQ-CLL16, EQ-5D-5L, and the remaining subscales/items from the EORTC QLQ-C30.

Subjects may continue to receive venetoclax for up to 2 years provided they continue to tolerate the drug, have no evidence of disease progression (based on Investigator's assessment), do not have unacceptable toxicity, and do not meet any of the criteria for discontinuation (Section 5.4.1). A final visit will be conducted upon treatment discontinuation.

After treatment discontinuation, subjects will be followed for disease progression (if progression has not already occurred) and survival. Post-treatment calls will be performed every 6 months until discontinuation from the study. Survival information (i.e., the date and cause of death, post-treatment cancer therapies, date of progression, etc.) will be collected. This period will continue for 2 years following discontinuation of venetoclax.

All study procedures will be performed as outlined in Section 5.3.1.1 and [Appendix D](#) and [Appendix E](#).

For subjects who continue to derive benefit after 2 years of treatment, AbbVie will work with the investigator on a case by case basis to consider the potential continuation of venetoclax therapy. In countries where venetoclax is commercially available, extension of therapy may not be allowed.

A safety analysis will be performed for all subjects participating in the study who took at least one dose of study drug. For the study as a whole, serious adverse events and adverse events will be evaluated and summarized. Laboratory test results and vital signs will be explored for trends and summarized.

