A CT scan with contrast will be accepted if previously performed within 35 days prior to the first dose of venetoclax. Otherwise, a CT scan must be performed within the Screening window (28 days) for all subjects. A CT scan will be performed for all subjects at Week 48 to confirm disease response. Contrast-enhanced CT scans including neck, chest, abdomen, and pelvis will be performed to assess response to treatment. A contrast-enhanced MRI of the neck, chest, abdomen and pelvis with a non-contrast CT scan of the chest may be used for subjects in whom a contrast CT is medically contraindicated (i.e., subjects with a severe allergy to CT contrast agents or subjects with impaired renal clearance). Whichever method is used at Screening should be consistently used throughout the duration of the study.

Any CT scan (or MRI) performed as standard of care throughout the study should be captured on the eCRF.

NOTE: CT scans (or MRI) may be performed 7 days prior to the scheduled visit.

Bone Marrow Aspirate and Biopsy

At baseline, a bone marrow aspirate and biopsy are not required; however results should be recorded if available. If the subject achieves a CR by clinical criteria and confirmatory CT scan, a bone marrow aspirate and biopsy will be performed to confirm the CR. If a CT scan is performed and does not confirm a CR, a bone marrow biopsy should not be obtained.

Bone marrow aspirates and biopsies performed as standard of care throughout the study should also be captured on an eCRF.

Final Visit

Upon treatment discontinuation (Section 5.4.1), the reason(s) for discontinuation will be recorded in the eCRFs and a Final Visit will be performed. The Final Visit procedures as listed in [Appendix D](#) and [Appendix E](#) should be performed as soon as possible after study drug discontinuation.

At the Final Visit all used/unused study drug are to be returned to the site and drug accountability performed.

30-Day Safety Visit

A 30 day Safety Follow-up Visit should be performed approximately 30 days (\pm 3 days) following the last dose of venetoclax (to allow for AE collection 30 days following last dose of study drug). Refer to [Appendix D](#) and [Appendix E](#) for procedures to be performed.

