6.1.9.2 Dose Modifications Based on Toxicities

Dosing interruption and/or dose reduction may be required. See [Table 7](#) for dose modifications for hematologic and other toxicities related to venetoclax. For subjects who have had a dosing interruption greater than 1 week during the first 5 weeks of dose titration or greater than 2 weeks when at the daily dose of 400 mg, TLS risk should be reassessed to determine if restarting at a reduced dose is necessary (e.g., all or some levels of the dose titration).

Tumor Lysis Syndrome

If a subject experiences blood chemistry changes suggestive of TLS, the following day's venetoclax dose should be withheld. If resolved within 24 to 48 hours of last dose, treatment with venetoclax can be resumed at the same dose. For events of clinical TLS or blood chemistry changes requiring more than 48 hours to resolve, treatment should be resumed at a reduced dose ([Table 7](#) and [Table 8](#)). When resuming treatment with venetoclax after interruption due to TLS, the instructions for Prophylaxis for tumor lysis syndrome should be followed.

Other Toxicities

Treatment with venetoclax should be withheld for any grade 3 or 4 non-haematological, grade 3 or 4 neutropenia with infection or fever, or grade 4 haematological toxicities, except lymphopenia. To reduce the risk of infection associated with neutropenia, granulocyte-colony stimulating factor (G-CSF) may be administered with venetoclax if clinically indicated. Once the toxicity has resolved to grade 1 or baseline level (recovery), therapy with venetoclax may be restarted at the same dose. If the toxicity recurs, and for any subsequent occurrences, the dose reduction guidelines in [Table 7](#) and [Table 8](#) should be followed when resuming treatment with venetoclax following resolution. A larger dose reduction may occur at the discretion of the investigator. For subjects who require dose reductions to less than 100 mg for more than 2 weeks, due to adverse events, discontinuation of venetoclax should be considered.

Table 7. Recommended Dose Modifications for Toxicities

Event	Occurrence	Action
Tumor Lysis Syndrome		
Blood chemistry changes or symptoms suggestive of TLS	Any	Withhold the next day's dose. If resolved within 24 – 48 hours of last dose, resume at the same dose.
		For any blood chemistry changes requiring more than 48 hours to resolve, resume at a reduced dose (Table 8)

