8.1.3 Timing of Study Endpoints and Safety Evaluations

The date the last enrolled subject has completed their Week 48 quality of life and disease assessments, or after all enrolled subjects have discontinued venetoclax, whichever is earlier, will be defined as the data "cutoff" date for the analyses. Quality of life, efficacy and safety data up to and including this date will be collected. Exact data cutoff date for the analysis will be detailed in the SAP which will be signed off prior to the data cut-off date. During this data collection period, active subjects will continue to receive venetoclax, as applicable. When data collection is complete and all data management quality assurance (QA) and quality control (QC) procedures are performed, the clinical database data will be extracted for documentation and statistical analyses. Any active subjects will continue to receive venetoclax until they discontinue or for up to 2 years. Once the last enrolled subject discontinues/completes the study, the study will be considered complete and all remaining data will be collected and entered into the clinical database.

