- u. ECOG performance status may be performed within 72 hours before or after the scheduled visit starting with Week 24.
- v. Survival information includes i.e., the date/cause of death, post treatment cancer therapies, etc.
- w. In countries where venetoclax is not commercially available, subjects who continue to derive benefit after 2 years of treatment may be able to extend their treatment for up to 2 additional years. AbbVie will work with the investigator on a case by case basis to consider the potential continuation of venetoclax therapy. Subjects who participate in the 2 year Extended Access phase will have study drug assigned at Week 108. For patients that are not participating in the 2 year Extended Access phase the Week 108 visit is the Final visit. The specific study assessments to be performed at the Extended Access visits are detailed in [Appendix E](#), Study Activities.

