4.2 Study Design and Plan

This is an open-label, single arm, Phase 3b, multi-center study evaluating the impact of venetoclax monotherapy on the quality of life in relapsed/refractory CLL.

This study is designed to enroll approximately 200 subjects to meet scientific objectives without enrolling an undue number of subjects in alignment with ethical considerations.

Subjects meeting the eligibility criteria will be treated with venetoclax once daily (QD), continuously up to 2 years provided they continue to tolerate the drug, have no evidence of disease progression (based on Investigator's assessment), do not have unacceptable toxicity, and do not meet any of the protocol specified criteria for discontinuation.

Dosing Schedule Overview

Venetoclax is administered orally once daily (QD), continuously. To mitigate the risk for tumor lysis syndrome (TLS), a lead-in period (up to 5 weeks) is employed to evaluate a step wise dose-titration as specified in the protocol, and [Figure 1](#).

Figure 1. 5-Week Dose-Titration Schedule

Week	VENETOCLAX Daily Dose
1	20 mg
2	50 mg
3	100 mg
4	200 mg
5 and beyond	400 mg

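### SAP Table 2 puts Rx Days 742-743 in both the Week 96 and the Week 108 window, and the two-year and Week 108 statements of when treatment ends need reconciling

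*Protocol*

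**What the plan says.** **Duration of treatment.** Protocol Section 5.1 states that "Subjects may continue to receive venetoclax for up to 2 years provided they continue to tolerate the drug". Section 8.1.3 repeats the limit ("Any active subjects will continue to receive venetoclax until they discontinue or for up to 2 years"), as do the synopsis and SAP Section 4.2 ("continuously up to 2 years provided they continue to tolerate the drug").

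**End of treatment by visit schedule.** Section 5.1 also says of study visits that from Week 48 "they will be reduced to every 3 months until the end of study treatment (Week 108", and of the questionnaires that they are given at Week 48, "then every 12 weeks thereafter until the end of study treatment (Week 108". Appendix D, footnote w, adds: "For patients that are not participating in the 2 year Extended Access phase the Week 108 visit is the Final visit". Section 5.3.1.1 says that the Final Visit procedures "should be performed as soon as possible after study drug discontinuation".

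**Analysis windows.** SAP Section 6.3, Table 2, assigns quality-of-life forms to visits by Rx day. Week 96 is nominal Day 666 with window 658 to 743. Week 108 is nominal Day 750 with window 742 to 825. If several forms fall in one window, the smallest score is used, and the largest in a sensitivity analysis. A separate Final Observation row takes the last non-missing value within 30 days of the last dose. SAP Sections 10.2.1 and 10.2.2 report Week 108 and the Final visit as one time point.

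**The concern.** A window table should send each form to exactly one visit. Days 742 and 743 belong to two, and the SAP has no rule for that case. The smallest-score rule chooses among forms within one window. The rule based on distance to the nominal day excludes quality-of-life measures. As written, one form would be counted at both Week 96 and Week 108.

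The second matter is that treatment has two end descriptions and no passage converts one into the other. If any completer is seen at a literal two years, Table 2 places that form in Week 96. There it competes with the scheduled Week 96 form, and only the smaller score is kept. At stake are the late descriptive quality-of-life summaries and a single clear statement of the maximum treatment period.

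**Working it through.** **1. Reproduce the printed nominal days.** First dose is Rx Day 1 and there is no Day 0 (SAP Section 6.2), so Week W Day 1 = 7 × (W − 1) + 1. Width = last day − first day + 1.

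| Visit | Printed day | Formula | Window | Width |
|---|---|---|---|---|
| Week 4 | 22 | 22 | 2-43 | 42 |
| Week 8 | 50 | 50 | 44-71 | 28 |
| Week 12 | 75 | **78** | 72-153 | 82 |
| Week 24 | 162 | 162 | 154-237 | 84 |
| Week 36 | 246 | 246 | 238-321 | 84 |
| Week 48 | 330 | 330 | 322-405 | 84 |
| Week 60 | 414 | 414 | 406-489 | 84 |
| Week 72 | 498 | 498 | 490-573 | 84 |
| Week 84 | 582 | 582 | 574-657 | 84 |
| Week 96 | 666 | 666 | 658-**743** | **86** |
| Week 108 | 750 | 750 | 742-825 | 84 |

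The formula reproduces every nominal day except Week 12.

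**2. Overlap.** Every window starts the day after the previous one ends, except Week 108, which starts on Day 742 while Week 96 runs to Day 743. Days 742 and 743 are therefore shared. With Week 96 ending at Day 741, its width is 741 − 658 + 1 = 84 and Week 108 follows with neither gap nor overlap.

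**3. Scheduled visits.** With the ±2-day visit window of Protocol Section 5.1, Week 96 falls on Days 664-668 and Week 108 on Days 748-752. Neither range touches Days 742-743. Only an off-schedule or early-termination form can land there.

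**4. Two years against Week 108.** Two calendar years are 2 × 365 = 730 days (731 with a leap day). This is calendar arithmetic; the documents print only Day 750. The difference is 750 − 730 = 20 days (19 with a leap day).

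**5. Where a form near Day 730 would go.** Day 730 is 730 − 666 = 64 days after the Week 96 nominal day and 750 − 730 = 20 days before that of Week 108. Table 2 still sends it to Week 96, because the windows run 8 days before nominal and 75 days after (77 for Week 96). Days 731-741 map to Week 96 alone. Ending Week 96 at Day 741 does not change this; a mapping rule is needed.

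**6. Week 12.** The window 72-153 contains both Day 75 and Day 78, and form selection uses the smallest score rather than distance from nominal. The wrong nominal day has no effect on which form is chosen.

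**The case against.** The strongest reply is that the documents use two years as a rounded name for the Week 108 schedule. Section 5.1 has both terms. Footnote w of Appendix D ties benefit after two years to drug assignment at Week 108. The two-year Extended Access phase in Appendix E runs from Week 108 to Week 216, which is 108 × 7 = 756 days and again longer than two calendar years. No passage schedules a stop or a visit at Day 730, and dispensing every 12 weeks from Week 60 leads from Week 96 straight to Week 108. This stands as the likely intent, although no passage states it and Week 108 still exceeds the limit read literally.

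Two stronger readings are tempting, and the documents do not support either.

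- *A dosing gap before Extended Access.* A reader might count Days 731-749 as 19 undosed days and compare them with the interruption rule in Section 6.1.9.2 ("greater than 2 weeks when at the daily dose of 400 mg, TLS risk should be reassessed"). The gap arises only if a site applies a literal calendar limit against the dispensing schedule. Extended Access is described as continuing treatment, not restarting it. The gap is hypothetical, and the reassessment rule would already apply if it occurred.
- *Loss of Week 108 data.* A reader might infer that the Week 108 row loses all two-year completers. Forms from the scheduled Week 108 visit map only to Week 108. A form on Days 731-741 would need a completer's visit that Appendix D does not schedule. It would still appear in the Final Observation row, provided that it falls within 30 days of the last dose.

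**Conclusion.** The overlap in Table 2 is an error as written and depends on no interpretation: two Rx days, 742 and 743, belong to two visits. Its reach is small, because only off-schedule or early-termination forms can fall on those days.

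The two descriptions of the end of treatment differ by about 20 days on a literal reading. They look like loose wording rather than two intended rules, but the passages must be reconciled. Which description applies is for the sponsor to state.

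The placement of an end-of-treatment form in Week 96 is conditional: it matters only if a completer's form can fall before Day 742. The Week 12 nominal day is a minor correction. The Week 48 primary endpoint (window 322-405) and the sample size are unaffected.

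**What to change.** 1. In SAP Table 2, end the Week 96 window at Day 741.
2. In the same table, correct the Week 12 nominal day from 75 to 78.
3. Reconcile the two-year and Week 108 statements in the protocol synopsis, Sections 5.1 and 8.1.3, Appendices D and E, and SAP Section 4.2.
4. If the reconciled text allows a completer's end-of-treatment form before Day 742, add one sentence to SAP Section 6.3 that maps that form to the Week 108/Final visit time point of Sections 10.2.1 and 10.2.2. Changing the Week 96 boundary alone does not achieve this.

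The cost is two table entries, at most one added sentence and a wording clarification. No new data are needed and the sample size does not change.
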